4.1.1 Study Goals

This is a randomized, sham-controlled dose escalation and bioeffect study. The primary goal of the study is to evaluate the safety of the RD-X19 device in SARS-CoV-2 infected individuals with outpatient COVID-19 at two dosing schedules, and to assess the reduction of SARS-CoV-2 viral load in each dose group compared to sham controls. This is an efficacy hypothesis-generating study; sample size is based on convenience. However, there is adequate power to detect large differences in group SARS-CoV-2 reduction effects. The primary safety measure is absence of device-related serious adverse events or patterns of severity ≥ 2 device-related adverse events.

Safety and tolerability (local reactogenicity) will be assessed actively on each clinic visit by review of potential adverse events (AEs) and targeted physical examination, as required. Volunteers will be encouraged to contact designated clinical trial staff for AEs of a medically-urgent nature as soon as is practically possible and to seek immediate medical care, if needed.

Metabolic, liver, kidney and hematological laboratory evaluations will be performed at baseline and at Day 8 or early termination (and potentially during unscheduled) clinic visits. Methemoglobin assessments will be performed at baseline and Day 8.

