10.4.2 Safety Analyses

Summaries will be presented by treatment arm on the Safety Population. Adverse device effects will be coded using the latest version of the Medical Dictionary for Regulatory Activities (MedDRA). Treatment-Emergent Adverse Events (TEAE), vital signs, and methemoglobin will be summarized using descriptive statistics. Other safety data including prior and concomitant medications will be listed.

TEAE is any event not present prior to the initiation of the treatments or any event already present that worsens in either intensity or frequency following exposure to the treatments. Number and percent of subjects reporting TEAEs will be tabulated by treatment group. Summaries will be presented by system organ class and preferred term, and further by severity and relationship to study treatment. In the summaries of incidence rates (frequencies and percentages), severity and relationship to treatment, subjects who report more than one event that are mapped to the same

preferred term will be counted only once under the strongest severity and relationship, accordingly.

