5.6.2 Vital Signs

For each vital sign (systolic and diastolic blood pressure, heart rate, and oral temperature), actual values and change from baseline values will be summarized using descriptive statistics for each treatment group by visit.

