5.6.4 Other Assessments

Following assessment results will be presented in subject data listing: medical history, physical examination, clinical laboratory evaluations, concomitant medications.

Interim Analysis

Upon completion of all subjects in Cohort 1, an unblinded interim analysis will be conducted focusing on the following evaluations:

- Efficacy:
 - Geometric mean viral load as measured in saliva on day 1, 3, 5 and 8 by RT-qPCR
 - Proportion of subjects demonstrating viral load reduction $\geq 95\%$ on day 3, 5 and 8 by RT-qPCR.
 - Time to alleviation of COVID-19 signs and symptoms
 - Time to sustained alleviation of COVID-19 signs and symptoms
- Safety:
 - All safety tabulations as listed in section 5.6.1 will be assessed as part of the interim analysis.
 - Summary of Treatment Emergent Adverse Events including a review of listings to monitor:
 - Number of study subjects experiencing any Serious Adverse Reaction (SAE).
 - Number of study subject experiencing treatment site reactions, including pain, induration or erythema of the oropharynx or oral mucosa, including the uvula and tongue.
 - Number of study subjects with any laboratory result that is out-of-range using the testing laboratory's institutional standards, including blood, urine and methemoglobin measured by pulse oxymetry.
 - Number of subjects experiencing laryngospasm, bronchospasm or anaphylaxis within 2 hours after use of the RD-X19 Device that is considered related to RD-X19.
 - Number of subjects experiencing an allergic reaction such as generalized urticaria (defined as occurring at three or more body parts) within 72 hours after use of study treatment that is considered related to RD-X19.
 - Number of subjects experiencing Grade 3 TEAE, in the same SOC grouping of PT, considered to be related to RD-X19.

As study subjects in cohort 1 are essentially a separate study, there is no prohibition to sponsor being unblinded for the interim analysis. Cohort 1 subjects are not tied to cohort 2 in any way and unblinding data from cohort 1 has no operational or statistical implications for cohort 2 assessment by sponsor. Study site personnel may not be unblinded to cohort 1 as there is a reasonable possibility that this information could be the basis for bias in the assessment of cohort 2.

To meet above review interest, the following summary tables (treatment groups: 4 Days RD-X19 vs. Sham) and by-subject data listings will be prepared for the interim analysis:

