16.2.5.2	Treatment Record and Subject Diary Collection at End of Study
16.2.5.3	Treatment Application Log
16.2.6.1.1	COVID-19 Symptom Assessment and Severity Score
16.2.6.1.2	COVID-19 Symptom Assessment and Severity Score from Subject Diary
16.2.6.2	Clearance of COVID-19 Symptoms
16.2.6.3	Viral Load via Saliva Specimen and Oropharyngeal Swab Collection
16.2.6.4	Derived Clearance of Viral Infection and Time-Weighted Average Change from Baseline in Log10-Transformed Viral Load via RT-qPCR
16.2.7	Adverse Events
16.2.8.1	Out-of-Range Results of Clinical Laboratory Tests
16.2.8.2	Pregnancy Test (Female Subjects Only)
16.2.9.1	Reactogenicity Assessment
16.2.9.2	Oropharyngeal Assessment
16.2.9.3	Vital Signs
16.2.9.4	Physical Examination
16.2.9.5	Prior and Concomitant Medications
16.2.9.6	Methemoglobin Measurement

List of Figures

Number	Description	Analysis Set
15.1.1	Kaplan-Meier Plot of Time to Clearance of Viral Infection	ITT Population
15.1.2	Kaplan-Meier Plot of Time to Clearance of Viral Infection	PP Population
15.2.1	Kaplan-Meier Plot of Time to Alleviation of COVID-19 Symptoms	ITT Population
15.2.2	Kaplan-Meier Plot of Time to Alleviation of COVID-19 Symptoms	PP Population
15.3.1	Kaplan-Meier Plot of Time to Sustained Alleviation of COVID-19 Symptoms	ITT Population
15.3.2	Kaplan-Meier Plot of Time to Sustained Alleviation of COVID-19 Symptoms	PP Population

Summary Tables

Table 14.1.1 – Subject Final Study Disposition

	Treatment Group			Total n (%)
	4 Days RD-X19 n (%)	7 Days RD-X19 n (%)	Sham n (%)	
Subjects Randomized	XX	XX	XX	XX
Subjects Completed Study	XX (XX.X)	XX (XX.X)	XX (XX.X)	XX (XX.X)
Subjects Discontinued	XX (XX.X)	XX (XX.X)	XX (XX.X)	XX (XX.X)
Reason for Discontinuations:				
Withdrawal by Subject	XX (XX.X)	XX (XX.X)	XX (XX.X)	XX (XX.X)
Adverse Event	XX (XX.X)	XX (XX.X)	XX (XX.X)	XX (XX.X)
Medication Code Unblinded	XX (XX.X)	XX (XX.X)	XX (XX.X)	XX (XX.X)
Lost to Follow-Up	XX (XX.X)	XX (XX.X)	XX (XX.X)	XX (XX.X)
Pregnancy	XX (XX.X)	XX (XX.X)	XX (XX.X)	XX (XX.X)
Physician Decision	XX (XX.X)	XX (XX.X)	XX (XX.X)	XX (XX.X)
Failure to Meet Entry Criteria	XX (XX.X)	XX (XX.X)	XX (XX.X)	XX (XX.X)
Other	XX (XX.X)	XX (XX.X)	XX (XX.X)	XX (XX.X)

Source: Listing 16.2.1

O:\Studies\EmitBio\EB-P12-01\Biometrics\Programs\Tables\xxx.sas ran on Month Day, Year at hh:mm on data from Month Day, Year.

Table 14.1.2 – Subject Population

	Treatment Group			Total n (%)
	4 Days RD-X19 n (%)	7 Days RD-X19 n (%)	Sham n (%)	
Randomized	XX	XX	XX	XX

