				Date (Study Day)	Time					
Treatment:										

Study Day is calculated relative to date of first treatment. Day 1 is the day of first treatment.

O:\Studies\ EmitBio\EB-P12-01\Biometrics\Programs\Listings\xxx.sas ran on Month Day, Year at hh:mm on data from Month Day, Year

Listing 16.2.6.4 – Derived Clearance of Viral Infection and Time-Weighted Average Change from Baseline in Log10-Transformed Viral Load via RT-qPCR

Subject	Cohort	Analysis	Clearance of Viral Infection (Study Day)				Change from Baseline in Log10-Transformed Viral Load (Study Day)			TWA Change from Day 1 to Day 8
			Visit 2 /Day 2	Visit 3 /Day 3	Visit 4 /Day 5	Visit 5 /Day 8	Visit 3 /Day 3	Visit 4 /Day 5	Visit 5 /Day 8	
Treatment:										
	ITT		No (2)	No (3)	No (5)	No (9)	xx.x (3)	xx.x (5)	xx.x (9)	xx.x
	PP		No (2)	No (3)		No (9)	xx.x (3)		xx.x (9)	xx.x

Abbreviation: ITT = Intent-to-Treat, PP = Per-Protocol, TWA = Time-Weighted Average, LOCF = Last observation carried forward
Study Day is calculated relative to date of first treatment. Day 1 is the day of first treatment.

For the ITT analysis, missing viral load will be imputed using the LOCF method.

Note 1: Clearance of viral infection is defined, based on viral load via RT-qPCR, as achievement of: [1] RP Ct ≥ 0 , AND [2] Average N1 Ct ≥ 32 or Average N1 Ct = “Undetermined”.

Note 2: TWA Change from Day 1 to Day 8 is calculated using the trapezoidal rule.

O:\Studies\ EmitBio\EB-P12-01\Biometrics\Programs\Listings\xxx.sas ran on Month Day, Year at hh:mm on data from Month Day, Year

Listing 16.2.7 - Adverse Events

Subject	Cohort	AE No.	System Organ Class / Preferred Term / Event Name	Occurred prior to first dose?	Start Date (Study Day)	Stop Date (Study Day)	Serious AE?	Intensity	Causality to Study Device	Action Taken	Outcome
Treatment:											

Note: Adverse events coded in MedDRA, version xx.x

Study Day is calculated relative to date of first treatment. Day 1 is the day of first treatment while Day -1 is the day prior to first treatment.

O:\Studies\EmitBio\EB-P12-01\Biometrics\Programs\Listings\xxx.sas ran on Month Day, Year at hh:mm on data from Month Day, Year

Listing 16.2.8.1 – Out-of-Range Results of Clinical Laboratory Tests

Subject	Cohort	Visit	Lab Panel	Test Name	Result	Flag	Out of Range: NCS or CS
---------	--------	-------	-----------	-----------	--------	------	-------------------------

Treatment:

Abbreviation: CS = clinically significant, NCS = not clinically significant

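### CMP and CBC results are planned as listings only, with no by-arm summary of values or change from baseline, so a consistent group shift that stays in range or is not judged clinically significant would go unseen

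*Combined protocol and SAP*

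**What the plan says.** Safety is one of the trial's primary goals (protocol 4.1.1, 6.1 and 10.1), and SAP 3.1 counts clinical laboratory tests among the safety assessments. The data are paired: "Metabolic, liver, kidney and hematological laboratory evaluations will be performed at baseline and at Day 8 or early termination" (protocol 4.1.1).

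The planned presentation is as follows.

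- SAP 5.6.4: "Following assessment results will be presented in subject data listing: medical history, physical examination, clinical laboratory evaluations, concomitant medications".
- Protocol 10.4.2: "Treatment-Emergent Adverse Events (TEAE), vital signs, and methemoglobin will be summarized using descriptive statistics", and then "Other safety data including prior and concomitant medications will be listed". CMP and CBC are not in the summarised group.
- SAP 7.2: the one CMP/CBC listing is 16.2.8.1, titled "Out-of-Range Results of Clinical Laboratory Tests". Its shell has columns for the result, a flag and "Out of Range: NCS or CS", under a treatment heading.
- SAP interim analysis (after 5.6.4): one item is "Number of study subjects with any laboratory result that is out-of-range", for Cohort 1.
- SAP 5.6.2, for vital signs: "actual values and change from baseline values will be summarized using descriptive statistics for each treatment group by visit". SAP 5.6.3 gives methemoglobin the same treatment at baseline and Day 8/ET.

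**The concern.** A laboratory effect of a device can appear as a modest movement in most treated subjects, rather than as a few extreme values. Such a movement shows in group means and changes from baseline. It shows poorly in a list of values that crossed a reference limit, and a by-subject listing is not a comparison with sham. If the plan is followed as written, the report could state that no laboratory signal was seen while the paired data already in the database contain one. The plan gives no reason for handling CMP and CBC differently from vital signs, which are measured at the same two visits.

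**Working it through.** **Step 1: trace each route by which a CMP or CBC value could reach an output.**

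| Route | Shows in-range values? | Shows change from baseline by arm? |
|---|---|---|
| Tables 14.3.1.1 to 14.3.1.4 (TEAEs) | No; only findings recorded as AEs | No |
| Tables 14.3.2 to 14.3.5 (reactogenicity, oropharynx, vital signs, methemoglobin) | CMP/CBC not covered | CMP/CBC not covered |
| Listing 16.2.8.1 | No; out-of-range only | No |
| Interim count, Cohort 1 | No; any out-of-range result | No |

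Under protocol 9.1.2 (version 2.0), a post-treatment laboratory finding becomes an AE if it is clinically significant. A group shift inside the reference range would not normally meet that test. Change from baseline cannot be rebuilt from Listing 16.2.8.1 either, because a subject with one or both values in range lacks the pair.

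**Step 2: compare text with listing.** SAP 5.6.4 places laboratory evaluations in a listing without restriction. The restriction comes only from the title and shell of 16.2.8.1. The two do not match.

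**Step 3: illustrate what is lost.** The plan has no figure to reproduce: the sample size is one of convenience (SAP 3.2), and no laboratory SD, effect size or test is given. From the documents: 20 RD-X19 and 10 sham per cohort, hence 20 v 10 within a cohort, or 20 v 20 when the sham groups are pooled as in the ANCOVA code of SAP 5.5.1. Assumed: a normal analyte; a 95% reference range, so 5% of sham values are out of range; a true shift of d SD; baseline to Day 8 correlation r of 0 or 0.5; two-sided 5% level.

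Probability that an active subject is out of range: p1 = P(|Z + d| > 1.96).

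- d = 0.5: p1 = 0.079, so 20 × 0.079 = 1.6 expected of 20.
- d = 1.0: p1 = 0.170, so 20 × 0.170 = 3.4 expected of 20. Pooled sham: 20 × 0.05 = 1.0 of 20.

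So even a full 1 SD shift leaves about 83% of treated subjects in range.

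Power for out-of-range counts is the exact Fisher power, enumerated over all outcomes. Power for baseline-adjusted change uses the noncentral t with residual SD √(1 − r²), noncentrality d / [√(1 − r²) × √(1/n1 + 1/n0)] and n1 + n0 − 3 degrees of freedom. Example, 20 v 10, d = 1, r = 0.5: √0.75 × √(0.05 + 0.10) = 0.866 × 0.387 = 0.335; noncentrality 1/0.335 = 2.98 on 27 df; power 82%.

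| Shift | Comparison | Out-of-range counts | Change, r = 0 | Change, r = 0.5 |
|---|---|---|---|---|
| 1 SD | 20 v 10 | 0.8% | 70% | 82% |
| 1 SD | 20 v 20 | 10% | 87% | 94% |
| 0.5 SD | 20 v 10 | 0.3% | 24% | 30% |
| 0.5 SD | 20 v 20 | 0.7% | 34% | 43% |

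**The case against.** The strongest defence is that the SAP follows its protocol. Protocol 10.4.2 names what is summarised and sends the rest to listings. Mean change in methemoglobin is a named endpoint in protocol Table 1; CMP and CBC are not. Laboratory harm that matters also has routes into view: clinically significant findings enter the by-arm TEAE tables, and Grade 3 device-related laboratory abnormalities count toward the pausing rule (protocol 8.5.1). All of this stands. It narrows the gap to shifts that stay in range or are not judged clinically significant, but does not close it.

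The SAP also describes its shells as examples open to modification (section 6). A table could therefore be added, but none is pre-specified, and the sponsor may already be unblinded to Cohort 1.

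The power figures are open to fair attack. The shift size is assumed, and the documents give reasons to expect little systemic effect: local illumination, target tissue penetration under 0.5 mm, and no laboratory AEs over 14 days in 25 healthy volunteers. SAP 5.1 says the study is not powered for testing, and no Fisher test of flags is planned. The powers are per analyte: if 30 analytes were assumed and Bonferroni applied, the 1 SD power at r = 0.5 would fall to 33% (20 v 10) and 60% (20 v 20). A 95% reference range may not describe acutely infected subjects. The figures therefore show information lost and nothing more.

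Three stronger readings are tempting and are not supported. First, that every result is reduced to an in-range or out-of-range flag: the listing shell keeps the numeric result under a treatment heading, and SAP 5.6.4 sets no out-of-range limit. Second, that the primary goal is safety against sham: in protocol 4.1.1 the comparison with sham attaches to viral load reduction, and the primary safety measure concerns device-related SAEs and patterns of grade 2 or higher events. Third, that laboratory harm in general would be invisible: the AE route and the interim count rule that out.

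**Conclusion.** The point holds as a gap in planned safety reporting. No planned output shows in-range CMP or CBC values, or their change from baseline by arm, although both time points are collected and safety is a primary goal. Separately, SAP 5.6.4 and Listing 16.2.8.1 disagree on which results are listed. Both conclusions rest on the documents alone.

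The size is illustrative and depends on the assumptions above. Within one cohort, a 1 SD shift would be picked up about 1% of the time from out-of-range counts, against 70% to 82% from baseline-adjusted change; at 0.5 SD it is under 1% against 24% to 30%. This is a worthwhile, inexpensive improvement to safety reporting, not a defect in the trial's primary analysis.

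**What to change.** 1. Take CMP and CBC out of the listing-only sentence in SAP 5.6.4.
2. Add one descriptive table in the format of Table 14.3.5: for each analyte and treatment group, the actual value at baseline and at Day 8/ET, and the change from baseline. Convert units to a common set across the local laboratories.
3. Make Listing 16.2.8.1 show all CMP and CBC results with the out-of-range flag kept, and retitle it, so that it agrees with SAP 5.6.4.
4. Optionally add the difference from sham with a 95% CI, labelled descriptive in line with SAP 5.1. Table 14.3.5 itself has no such column, so this goes beyond its format.

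The cost is SAP wording, one programmed table and unit conversion. No new sample, visit or subject burden is needed. With many analytes some differences will arise by chance; if intervals are added, about 1 in 20 will exclude zero when there is no effect, which is why the descriptive label is needed.

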- Review all pre-study medications, vitamins, supplements, and therapies up to 14 days prior to the start of screening that could impact the use of, or response to, the device and record on the appropriate e-CRF. Subjects are allowed to use over-the-counter medications and remedies to alleviate symptoms (e.g. acetaminophen, ibuprofen, cough drops, etc. and should be recorded.)
- Measure vital signs (HR, BP, **RR**, and oral temperature) and height and weight for determination of BMI.
- Perform full physical examination which will include assessments of the following organs and organ systems: skin, head, ears, eyes, nose, and throat (HEENT), neck, lungs, heart, liver, spleen, abdomen, extremities, lymph nodes (axillary and cervical), and nervous system.
- Obtain blood and urine for clinical screening laboratory evaluations:
 - Comprehensive Metabolic Panel (fasting or non-fasting)
 - CBC with differential
 - Urine pregnancy test (in women of childbearing potential)
- Review inclusion and exclusion criteria.

The overall eligibility of the subject to participate in the study will be assessed once all screening values are available. The screening process can be suspended prior to complete assessment at any time if exclusions are identified by the study team.

Study subjects who qualify for inclusion will be immediately randomized for their day 1 visit.

If a physiologic parameter, e.g., vital signs, is outside of the protocol-specified range, then the measurement may be repeated once if, in the judgment of the participating clinical site PI or appropriate sub-investigator, the abnormality is the result of an acute, short-term, rapidly reversible condition (e.g., stress, anxiety or “white coat syndrome”) or other source of error. A physiologic parameter may also be repeated if there is a technical problem with the measurement caused by malfunctioning, or an inappropriate measuring device (i.e., inappropriate-sized BP cuff).

A subject may be re-screened if there is a transient disease status (e.g., absent signs and symptoms associated with mild COVID-19), or if a protocol eligibility criterion that is not met at the initial time of screening, will be met by rescreening of all assessments within the next 2 days using the same subject number.

No subjects may be screened more than twice due to a screening failure result as defined above.

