9.1.2 Procedures for Abnormal Clinically Significant Laboratory Values or Findings

If in the judgement of the PI the finding poses a previously unknown risk to the subject or leads to a diagnosis of a disease or condition that would have been disqualified the subject for enrollment, the subject will be withdrawn from the study immediately.

All clinically significant findings that occur post randomization and after the first use of the RD-X19 device will be considered AEs. Clinically significant lab findings based on Visit 1 lab draws are considered Medical History and not Adverse Events.

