Tables / Listing	Description	Population
Efficacy		
Table 14.1.3	Demographic and Baseline Characteristics	Safety Population Cohort 1
Table 14.2.1.1	Time-Weighted Average Change in Log10-Transformed Viral Load by RT-qPCR from Baseline to Day 8	ITT Population of Cohort 1
Table 14.2.2.1	Log10-Transformed Viral Load via RT-qPCR by Visit	ITT Population of Cohort 1
Table 14.2.2.3	Proportion of Subjects with At Least 95% Reduction by Visit in SARS-CoV-2 Viral Load via RT-qPCR	ITT Population of Cohort 1
Table 14.2.5.1	Time to Alleviation of COVID-19 Symptoms	ITT Population of Cohort 1
Table 14.2.5.2	Time to Sustained Alleviation of COVID-19 Symptoms	ITT Population of Cohort 1
Safety		
Table 14.3.1.1	Treatment-Emergent Adverse Events by System Organ Class and Preferred Term	Safety Population of Cohort 1
Table 14.3.1.2	Treatment-Emergent Adverse Events by System Organ Class, Preferred Term and Severity	Safety Population of Cohort 1
Table 14.3.1.3	Treatment-Emergent Adverse Events by System Organ Class, Preferred Term and Causality to Study Device	Safety Population of Cohort 1
Table 14.3.2	Reactogenicity by Visit	Safety Population of Cohort 1
Table 14.3.3	Oropharyngeal assessment by Visit	Safety Population of Cohort 1
Listing 16.2.7	Adverse Events	Cohort 1 subjects
Listing 16.2.8.1	Out-of-Range Results of Clinical Laboratory Tests	Cohort 1 subjects
Listing 16.2.9.1	Reactogenicity Assessment	Cohort 1 subjects
Listing 16.2.9.2	Oropharyngeal Assessment	Cohort 1 subjects
Listing 16.2.9.6	Methemoglobin Measurement	Cohort 1 subjects

6 Tables and Listings

The following is an example of tables, listings and figures that will be included in the clinical study report. They may be modified as needed during the data analyses.

7 Appendices

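### The interim count of subjects with any out-of-range laboratory result would flag most subjects in both arms by chance, and no planned table shows laboratory change from baseline by arm

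*Combined protocol and SAP*

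**What the plan says.** The Interim Analysis text that follows SAP 5.6.4 lists a "Number of study subjects with any laboratory result that is out-of-range" by the testing laboratory's own ranges, covering blood, urine and methemoglobin. It sits under the heading "Summary of Treatment Emergent Adverse Events including a review of listings to monitor". The item itself says nothing about visit, change from baseline, grade or clinical significance.

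Protocol 4.1.1 sets the timing: "Metabolic, liver, kidney and hematological laboratory evaluations will be performed at baseline and at Day 8 or early termination". Protocol 9.1.1 names the panels as "Comprehensive Metabolic Panel (fasting or non-fasting)" and "CBC with differential". The only urine test listed there, or in the schedule of activities, is the pregnancy test.

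On output, SAP 5.6.4 places clinical laboratory evaluations in a subject listing. The interim package contains Listing 16.2.8.1, "Out-of-Range Results of Clinical Laboratory Tests", and no laboratory table. The table list in SAP 7.2 has none either, although vital signs and methemoglobin both get change-from-baseline tables there. Protocol 9.1.2 makes clinically significant findings after first device use adverse events, and adds: "Clinically significant lab findings based on Visit 1 lab draws are considered Medical History and not Adverse Events".

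**The concern.** A subject-level count of any abnormal value among many analytes rises quickly with the number of values examined, even when nothing is wrong. If it is already high in both arms, a real effect of the device has little room to raise it.

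The definition is also open. Read literally, a Day 1 value taken before treatment qualifies. Read in the light of its heading, only later values might. Two programmers could produce different counts from the same data.

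The safety monitoring team uses this package to recommend whether Cohort 2 proceeds at the next planned dose or at a reduced frequency. A laboratory item added for that review ought to carry information about laboratory change.

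**Working it through.** The plan gives no rate, threshold or power for this count, so there is no stated figure to reproduce.

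**Inputs from the documents.** Two scheduled draws. Cohort 1 is 20 active and 10 sham; Clarification Memorandum #2 allows up to 36, which is 24 and 12 at 2:1.

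**Assumptions.** *k* = 20 to 35 analytes per draw. Reference ranges exclude a fraction *p* = 5% of unaffected people; 2.5% and 1% are also shown.

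**1. Chance of at least one out-of-range value, independent analytes.** One draw: 1 − (1 − p)^k. Two independent draws: 1 − (1 − p)^(2k).

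| p | k | One draw | Two draws |
|---|---|---|---|
| 5% | 20 | 64% | 87% |
| 5% | 29 | 77% | 95% |
| 5% | 35 | 83% | 97% |
| 2.5% | 20 to 34 | 40-58% | 64-82% |
| 1% | 20 to 34 | 18-29% | 33-50% |

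**2. Allowing for correlation (p = 5%, simulated normal values, between-visit correlation 0.5 to 0.8).**

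| k | Between-analyte correlation | One draw | Either of two draws |
|---|---|---|---|
| 20 | 0.3 | 54% | 71-76% |
| 20 | 0.5 | 42% | 57-63% |
| 29 | 0.3 | 65% | 81-86% |
| 29 | 0.5 | 50% | 67-72% |
| 34 | 0.3 | 70% | 85-89% |
| 34 | 0.5 | 53% | 70-76% |

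The 54% at the lower end of the one-draw range corresponds to 20 analytes with correlation 0.3, or 25 with 0.4. At correlation 0.5 a single draw flags 42-53%. Over two draws the lowest figure is 57%.

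**3. Room left for a treatment effect.** Let *q* be the background rate and *e* the fraction of active subjects truly affected. The active rate is 1 − (1 − q)(1 − e). With q = 0.95 and e = 0.5 this is 1 − 0.05 × 0.5 = 0.975: about 19.5 of 20 active against 9.5 of 10 sham. The SAP plans no test here, so two-sided 5% Fisher power is only a yardstick.

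| Background | Power at 20:10, e = 0.5 | Power at 24:12, e = 0.5 |
|---|---|---|
| 95% | 0.01 | 0.01 |
| 77% | 0.10 | 0.12 |
| 50% | 0.23 | 0.22 |
| 5% | 0.76 | 0.86 |

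**4. Would dropping the Day 1 draw be enough?** Counting subjects with any analyte in range on Day 1 and out of range at Day 8 still flags 30-76% of unaffected subjects across the step 2 settings and their zero-correlation counterparts (37-70% for 29 analytes). It would not be enough.

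**5. Counting by analyte.** For one analyte, the chance of moving from in range to out of range is at most 0.95 × 0.05 = 4.75%, or 20 × 0.0475 = 0.95 of 20 active and 0.475 of 10 sham. That is close to the 5% background row in step 3. Chance clusters remain possible: with Binomial(20, 0.0475), P(3 or more) = 0.067, so about 29 × 0.067 = 1.9 of 29 analytes would reach 3 of 20. The sham column is needed to read the table.

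**The case against.** A reader might infer that the escalation review cannot see a laboratory signal at all. The documents do not support that. Listing 16.2.8.1 gives visit, panel, test, result, flag and clinical significance, grouped by treatment. With 30 to 36 subjects and two scheduled draws, an unblinded reviewer can separate Day 1 rows from Day 8 rows. Clinically significant findings after first use are adverse events and enter the by-arm interim tables by severity and causality. Methemoglobin has its own interim listing and a final change-from-baseline table.

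A reader might also infer that the plan expressly counts pre-treatment draws. It neither includes nor excludes them, and the heading over the item refers to treatment-emergent events.

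The count also carries limited weight. It is not among the specific criteria for safety review in protocol 4.1.2 and 6.1, and no threshold is attached to it. Laboratory abnormalities reach the pausing rules in protocol 8.5.1 through related Grade 3 events.

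All of this stands and limits the severity. The gap that remains is narrower. The adverse-event route depends on an investigator judging each value significant. The listing leaves reviewers to tally by hand, does not show the baseline of a value that was in range, cannot distinguish in range from not drawn, and has no denominators. A modest, consistent shift judged not clinically significant in each subject would appear only there.

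**Conclusion.** The concern holds in this limited form: the count as defined is close to uninformative, and no planned summary, interim or final, shows laboratory change from baseline by arm with denominators.

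Its size rests on assumptions about analyte number, range width and correlation that the documents do not supply. The claim that most unaffected subjects are flagged over two draws survives correlation up to 0.5 and a 2.5% exclusion rate with independent analytes; it fails if ranges exclude only about 1% per analyte. Calling the count near its ceiling is fair only towards the upper end of the range. Abnormalities from COVID-19 itself would add to the background and are not included in these figures.

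Severity is minor to moderate. This is a cheap improvement to the presentation of data already collected, and no decision rule depends on it.

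**What to change.** - Redefine the interim item as the number and percent of subjects, by analyte and arm, who are in range at baseline and out of range at Day 8/ET. Add worsening by grade only if Appendix 2 grades those analytes; the public version says only that the appendix is available on request.
- Add a baseline-by-Day 8/ET shift table, by analyte and arm with denominators, to the interim package and to SAP 7.2. Keep Listing 16.2.8.1 alongside it.
- Delete urine from the item. Leave methemoglobin to its existing separate outputs.

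The cost is one extra programmed table and a wording change in the SAP. No new data are needed.
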